8.5. Subgroups

Subgroup analysis will not be conducted in this study, regarding the small sample size.

This document is confidential.

9. Demographic, Other Baseline Characteristics and Medication

9.1. Subject Disposition and Withdrawals

All subjects of the ITT population will be accounted for in this study.

Subject accounting will summarize subjects randomized and randomized but not treated for all subjects by overall and site.

Subject accounting by visit will be summarized by treatment group and overall at each visit (scheduled visits only).

Subject disposition will be summarized based on the ITT population by treatment and overall. Summaries will include subjects randomized, subjects randomized but not treated, subjects treated, subjects completed treatment, subjects discontinued treatment, primary reason for discontinuation of treatment (including summary of subjects who stopped treatment due to COVID-19), subjects completed the study, subjects discontinued from the study, primary reason for discontinuation from the study (including summary of subjects who discontinued due to COVID-19) and subjects completed Follow-up. Subjects who stopped treatment or discontinued study due to COVID-19 will be identified using other specify field in CRF.

Subject disposition will also be summarized by site on the ITT population.

Subjects in each analysis population (ITT, SAF, PP, POE analysis population) will be summarized by treatment group on the ITT population.

In addition, time (days since the first dose of study drug) to permanent discontinuation of study drug by reason for discontinuation will be displayed graphically in subjects having permanently discontinued from the study drug.

Randomization, study completion, drug completion, visit dates will be listed for the ITT population. Additional listings of discontinuation reason, missed visit and missed assessment for subjects who discontinued due to COVID-19 will be presented for the ITT population.

Analysis populations will be summarized and listed on the ITT population.

9.2. Demographic and Baseline Disease Characteristics

Summary statistics for demographic and other Baseline disease characteristics will be presented for the ITT, SAF, PP and POE analysis population.

Age (years), height (cm), weight (kg), and BMI (kg/m²) will be summarized using summary statistics for continuous variables. Age groups (18-65, and > 65), sex, region (Europe, North America, and Asia Pacific),

This document is confidential.

race, ethnicity, and smoking history will be summarized using the summary statistics for categorical variables. Weight will additionally be presented for each subgroup < 90 kg and \geq 90 kg as well as dosing regimen (1 or 2 injections).

The Baseline disease characteristics IGA, weekly average PP NRS, weekly SD NRS and baseline DLQI will be summarized. IGA, will be summarized as a categorical variable.

A summary table for the stratification factor dosing regimen will be provided to show any discrepancies between what was reported through Interactive Voice Response System (IVRS)/Interactive Web Response System (IWRS) versus eCRF data (at baseline visit).

All demographic and baseline disease characteristics data will be listed on the ITT population.

9.3. Medical History

Medical history will be collected only at baseline and will be coded using Medical Dictionary for Regulatory Activities (MedDRA, Version 25.0).

Medical history will be summarized by treatment group. The summary will include number and percentage of subjects reporting each system organ class (SOC) and preferred term (PT) and will be sorted alphabetically by SOC and descending frequency of PT within SOC in the Nemolizumab treatment group. Summary tables will be presented for the ITT population.

Medical history data listings will be presented by subject number, start date, stop date, SOC, and PT for the ITT population.

9.4. Medical and Surgical Procedure

Medical and surgical procedures will be coded using the latest version of Medical Dictionary of Regulatory Activities (MedDRA).

Prior medical and surgical procedures are defined as those which have been stopped before first treatment.

Concomitant medical and surgical procedures will be defined as those started or stopped on or after the first treatment, or were ongoing during the study. If a procedure is started before the first treatment but is ongoing or stopped on or after the first treatment, it will be considered concomitant.

- Procedures during treatment period will be defined from start of treatment till 4 weeks (\leq 28 days) after the last treatment or early discontinuation date whichever is earlier.
- Procedures during follow-up period is defined from post treatment period (4 weeks ($>$ 28 days) after the last treatment or early discontinuation date, whichever is earlier) to follow-up visit date.

This document is confidential.

If the stop date and 'ongoing' are missing then the procedure will be considered concomitant. If stop date is partially missing, the procedure will be considered concomitant unless the non-missing part of date proves it ended prior to the first treatment date.

The following medical and surgical procedures (prior and concomitant) will be summarized by treatment group using the number and percent of subjects reporting each SOC and PT and sorted alphabetically by SOC and descending frequency of PT within SOC in the Nemolizumab treatment group. Summary tables will be presented for the ITT population.

- Prior procedure
- Concomitant procedure during treatment period
- Concomitant procedure during follow-up period

Medical and surgical procedures listings will be presented by treatment group on the ITT population and sorted by subject number, start date, stop date, SOC, and PT.

9.5. Medication

Medications will be classified and summarized on the ITT population as follows:

Prior medications are defined as those which stop before the first injection of study drug during the study.

Concomitant medications are defined as those started, stopped or ongoing on or after the first injection of study drug.

- *Medication during treatment period* is defined from start of treatment till 4 weeks (<= 28 days) after the last treatment or early discontinuation date whichever is earlier.
- *Medication during follow-up period* is defined from post treatment period (4 weeks (> 28 days) after the last treatment or early discontinuation date, whichever is earlier) to follow-up visit date.

If the stop date and 'ongoing' are missing then the medication will be considered as concomitant medication.

If stop date is partially missing, the medication will be considered as concomitant unless the non-missing part of date proves it ended prior to the first treatment date.

Medications (prior, concomitant and prohibited medications) will be coded using Version B3 Sep2021 of the World Health Organization's Drug Dictionary (WHO DD). Preferred Anatomical Therapeutic Chemical (ATC) coding will be performed.

The following summaries by ATC level 2, ATC level 4 and preferred term (PT) will be produced on the ITT population. Subjects with more than one medication in a given ATC level and preferred name will be counted only once in that category. It will be sorted ATC level alphabetically and descending frequency in PT within ATC level term.

This document is confidential.

- Prior medication
- Concomitant medication during treatment period
- Concomitant medication during follow-up period
- Prohibited medication during treatment period
- Prohibited medication during follow-up period

All medications (prior and concomitant medications, prohibited medications) will be listed for the ITT population.

9.6. Extent of Exposure

Following parameters will be summarized:

- Treatment duration (in days) is calculated as follows, where date of first treatment is defined as the first day: [(date of last treatment – date of first treatment) + 1].
- Total dose administered (mg) will be calculated as the sum of all doses of study drug administered.
- Total dose planned (mg) will be calculated as the sum of all doses of study drug planned (dispensed) according to the treatment schedule of the treatment group.
- The number of subjects who missed at least one dose
- The number of subjects who missed at least one dose due to COVID-19
- The number of doses missed
- The number of doses missed due to COVID-19

Note: The missed dose due to COVID-19 are captured as other-reason reported in CRF.

9.7. Treatment Compliance

Treatment compliance will be assessed through the treatment records and drug dispensation logs. As study drug is administered in the clinic, treatment compliance will be overseen and documented by the investigator and study staff (using the treatment records and drug accountability records).

Treatment compliance (%) is calculated as the total number of actual injections / the total number of expected injections * 100. The total number of actual injections is counted based on collected study drug administration data. The total number of expected injections is counted based on the dosage schedule and dispensed as per protocol.

This document is confidential.

10. Efficacy

Unless otherwise stated, all efficacy analyses will be performed on the ITT population.

All efficacy variables will be summarized by treatment group at each analysis visit. The primary comparison of interest is Nemolizumab compared to placebo.

10.1. Primary Efficacy Endpoints

10.1.1. Primary Analysis of Primary Efficacy Endpoint

The primary endpoint is the time to relapse which is defined as meeting at least 1 of the following criteria:

- Increase in (weekly average of the) PP NRS score ≥ 4 points from baseline
- Increase in IGA score ≥ 2 points from baseline;

For primary endpoint, any subjects with missing data for PP NRS and IGA Score both at visit will be censored at the respective timepoint. If any one of PP NRS or IGA Score data is available for the visit, calculation for primary endpoint will be made using available results. If a subject has taken prohibited medication at any point of time during treatment period, then subject will be censored at the respective visit.

The primary endpoint will be analyzed using Cox proportional hazard model with treatment group, dosing regimen as a factor, and baseline PP NRS score and IGA score as covariates on ITT population. The estimated hazard ratio and the corresponding 95% CI will be presented. A supportive analysis also will be performed using Per-Protocol Population.

Kaplan-Meier survival plots will also be presented for time to relapse. The median time, 25th and 75th quantiles along with corresponding CI will be presented using ITT/PP.

Censoring rule for primary endpoint variable is as follows:

Situation	Date of Progression or Censoring	Outcome
Relapse as described	Date of Relapse	Event
Subject withdrawn without relapse	Date of last efficacy assessment (PP NRS and IGA) prior to withdrawal	Censored
Treatment Discontinuation	Date of last efficacy assessment (PP NRS and IGA) prior to Treatment Discontinuation	Censored
Prohibited medication without relapse	Date of last efficacy assessment (PP NRS and IGA) prior to prohibited medication	Censored
Completes the study without relapse	Date of Week 24 completion	Censored
No Efficacy assessment	Date of study Day 1	Censored

This document is confidential.

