**Table 8. Estimand of Primary Endpoint**

Treatment	Population	Endpoint	Intercurrent events	Summary measure
Randomized treatment with subcutaneous injections of nemolizumab or placebo at Week 0, 4, 8, 12, 16 and 20	All randomized subjects (intent-to-treat population)	Time to relapse meeting at least 1 of the defined criteria	Time to relapse will be censored at the last observation prior to treatment discontinuation or use of prohibited medication	Hazard ratio of nemolizumab and placebo

As the primary analysis, the time to relapse will be analyzed using Cox proportional hazard model with treatment group, dosing regimen as a factor, and baseline PP NRS score and IGA score as covariates. The estimated hazard ratio and the corresponding 95% CI will be presented. If the assumption of proportionality is not met, other appropriate methods will be used and documented in the SAP.

In addition, Kaplan-Meier survival plots will be presented for time to relapse. The median time, 25th and 75th percentiles, and the corresponding CI will be reported.

If a subject withdraws from the study, takes prohibited medication, or completes the study without any relapse, time to relapse response will be censored respectively at the time of the last efficacy assessment (PP NRS and IGA) prior to study withdrawal, use of prohibited medication, or the completion of the study. If a subject has no efficacy assessment after randomization, then time to relapse will be censored at Day 1.

For the purpose of efficacy analysis, subjects receiving any prohibited therapies will be censored from the primary analysis.

As a supporting analysis, the time to relapse will also be analyzed using the same methods in the per-protocol population.

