8.4. Visit Windows

Efficacy by-visit summaries will use the analysis visit. All visits including unscheduled and early termination visits will be windowed based on the analysis visit window in [Table 8-1](#) which is based on study day. If multiple measurements are taken within the same window, the one taken closest to the target study day will be used for the analysis. If there are multiple measurements with same difference from target day, the later assessment should be used for the analysis.

Table 8-1: Analysis Visit Window

Analysis Visit	Target Study Day	Visit Window (IGA)	Visit Window (DLQI)
Baseline	1	≤ 1	≤ 1
Week 4	29	2 to 42	N/A
Week 8	57	43 to 70	N/A
Week 12	85	71 to 98	N/A
Week 16	113	99 to 126	2 to 140
Week 20	141	127 to 154	N/A
Week 24	169	155 to 210	141 to 210
Week 32 Follow-up	225	>211	N/A

All daily diary efficacy data will be classified into analysis visits as described in [Table 8-2](#) considering the data during the 7 days immediately preceding the target day of analysis visit.

Analysis visit of diary (ePRO) data will be defined depending on the data collection as below.

Consecutive daily assessment:

For the evening assessments (PP NRS), the daily data collected up to Week 24 will be classified into analysis visits considering the data during the 7 days immediately preceding the target study day of analysis visit. Similarly, for the morning assessment (SD NRS, morning sleep diary), the 7 days data up to the target study day will be classified into analysis visit. Details of the analysis visit window are in [Table 8-2](#) below.

This document is confidential.

Table 8-2: Analysis Visit Window for Evening and Morning Assessments

Analysis Visit	Target Study Day of Analysis Visit	Visit Window for evening assessment (PP NRS, AP NRS)	Visit Window for morning assessment (SD NRS, morning sleep diary)
Baseline	1	-7 to -1	-6 to 1
Week 1	8	1 to 7	2 to 8
Week 2	15	8 to 14	9 to 15
Week 3	22	15 to 21	16 to 22
Week 4	29	22 to 28	23 to 29
Week 5	36	29 to 35	30 to 36
Week 6	43	36 to 42	37 to 43
Week 7	50	43 to 49	44 to 50
Week 8	57	50 to 56	51 to 57
Week 9	64	57 to 63	58 to 64
Week 10	71	64 to 70	65 to 71
Week 11	78	71 to 77	72 to 78
Week 12	85	78 to 84	79 to 85
Week 13	92	85 to 91	86 to 92
Week 14	99	92 to 98	93 to 99
Week 15	106	99 to 105	100 to 106
Week 16	113	106 to 112	107 to 113
Week 17	120	113 to 119	114 to 120
Week 18	127	120 to 126	121 to 127
Week 19	134	127 to 133	128 to 134
Week 20	141	134 to 140	135 to 141

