20.1. Example SAS Code

1. The Example SAS code for Time to Event and Hazard Ratio

```
proc lifetest data=analysis_data;
  time aval*cnsr(1);
  strata trtp;
run;

proc phreg data=analysis_data;
  class trtp stratum;
  model aval*cnsr(1)=trtp stratum;
run;
```

2. The example SAS code for CMH model is listed as below:

```
proc freq data=analysis_data;
  tables stratum*trt*resp/ cmh alpha=0.1;
run;
```

3. The example SAS code for MMRM model is listed as below:

```
proc mixed data = analysis_data;
  class stratum trtp avisit subjid;
  model chg = base stratum trtp avisit trtp*avisit/ ddfm=kr;
  repeated avisit / subject=subjid(trtp) type=un;
  lsmeans trtp/ cl diff;
  lsmeans trtp*avisit/ slice=avisit cl diff;
run;
```

4. The example SAS code for ANCOVA model is listed as below:

```
proc mixed data = analysis_data;
  class stratum trtp;
  model chg = base stratum trtp;
```

This document is confidential.

lsmeans trtp/ cl diff;

run;

This document is confidential.

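### SAP 10.1.1 gives two conflicting rules for a visit with both PP NRS and IGA missing; followed literally, one of them discards relapses observed after the gap

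*SAP*

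**What the plan says.** SAP 10.1.1 handles missing data in prose, then sets out a censoring table.

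- **Both scores missing:** "For primary endpoint, any subjects with missing data for PP NRS and IGA Score both at visit will be censored at the respective timepoint".
- **One score present:** "If any one of PP NRS or IGA Score data is available for the visit", relapse status is worked out from that score. The missing-data rule therefore applies only when both are absent.
- **Table:** a relapse is an event on its own date. A completer without relapse is censored at "Date of Week 24 completion". The only row about absent data is for subjects with no efficacy assessment at all, who are censored at Day 1. Nothing covers an intermittent gap.
- **Prohibited medication:** the prose reads "If a subject has taken prohibited medication at any point of time during treatment period, then subject will be censored at the respective visit"; the table reads "Date of last efficacy assessment (PP NRS and IGA) prior to prohibited medication".

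Protocol 14.3.1 censors at "the last efficacy assessment (PP NRS and IGA) prior to study withdrawal, use of prohibited medication, or the completion of the study". It adds Day 1 for subjects with no assessment after randomization, and does not list a missed visit. The SAP estimand (Table 7-2) names only treatment discontinuation and prohibited medication.

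**The concern.** This is the event and censoring status of the sole primary endpoint. The SAP's example code, "model aval*cnsr(1)=trtp stratum", takes one time and one flag per subject, so a programmer must choose a rule, and two programmers could build different primary datasets from the same section. Protocol 14 lets the SAP supersede the protocol, so the protocol cannot settle a conflict inside the SAP.

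The case can be foreseen. Protocol 9.4 asks subjects who miss a dose to return for all remaining visits, and the remote-visit list in Protocol Appendix 1 does not include IGA. If the diary is also short that week, both scores are missing and the subject may return later.

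At stake are observed relapses in a trial of about 40 subjects, and the placebo relapse curve. That curve bears directly on the primary objective, durability after withdrawal. The prose also censors at the missed visit itself, a date with no data.

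**Working it through.** **The two rules side by side**

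| Subject | Prose | Table |
|---|---|---|
| Both missing at Week 8, relapse seen at Week 12 | Censored, Week 8 | Event, Week 12 |
| Both missing at Week 8, completes without relapse | Censored, Week 8 | Censored, Week 24 |

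**Inputs.** The plan has no figure to reproduce: no power, event count, relapse rate or missing-data rate is given.

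- From the documents: about 40 subjects randomized 1:1 (Protocol 14.1 and 9.3.1; SAP 4.3 agrees, although SAP 4.1 says about 100), so 20 per arm; six post-baseline IGA visits (SAP 10.2.1); weekly PP NRS averages (SAP Table 8-2).
- Assumed: placebo relapse R = 50% by Week 24 at a constant hazard, and a both-missing rate p per clinic visit unrelated to relapse. If each score is missing at 5% of clinic visits, p lies between 0.05 × 0.05 = 0.25% (independent) and 5% (always together).

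**Relapses lost if all are first seen at clinic visits k = 1 to 6**

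P(k) = (1−R)^((k−1)/6) − (1−R)^(k/6); loss = Σ P(k)[1−(1−p)^k] / R.

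For p = 3%: 0.1091×0.0300 + 0.0972×0.0591 + 0.0866×0.0873 + 0.0771×0.1147 + 0.0687×0.1413 + 0.0612×0.1670 = 0.0454, and 0.0454/0.5 = 9.1%.

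**Relapses lost if all are first seen on the weekly diary, w = 1 to 24**

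P(w) = (1−R)^((w−1)/24) − (1−R)^(w/24); loss = Σ P(w)[1−(1−p)^floor(w/4)] / R. The missing-data rule still operates at clinic visits only.

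**Placebo Kaplan-Meier relapse at Week 24 under the prose (true value 50%)**

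- Clinic visits: 1−(1−h(1−p))^6, with h = 1−0.5^(1/6) = 0.1091.
- Weekly diary: 1−(1−g)^18 × (1−g(1−p))^6, with g = 1−0.5^(1/24) = 0.0285.

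| p | Lost, diary | Lost, clinic | KM, diary | KM, clinic |
|---|---|---|---|---|
| 0.25% | 0.6% | 0.8% | 49.98% | 49.91% |
| 1% | 2.4% | 3.1% | 49.91% | 49.63% |
| 3% | 6.9% | 9.1% | 49.74% | 48.89% |
| 5% | 11.3% | 14.7% | 49.56% | 48.13% |

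Of 10 placebo relapses, the clinic column loses 0.08, 0.31, 0.91 and 1.47. Changing R matters little: at p = 5% the clinic loss is 15.4% for R = 30% and 13.7% for R = 70%.

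**After the fix.** Relapses remain lost only when every visit from onset to Week 24 is missing: Σ P(k)p^(7−k)/R = 0.03%, 0.12%, 0.38% and 0.65% across the four rates, taking relapse to persist.

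**Hazard ratio.** In a 40,000-subject simulation with p = 5% in both arms and relapse of 60% (placebo) and 20% (nemolizumab), the hazard ratio was 0.240 under the table and 0.239 under the prose. Precision falls modestly. With 10 and 3 relapses (nemolizumab relapse 15%, assumed), the SE of the log hazard ratio is √(1/10+1/3) = 0.658; after the clinic-visit losses it becomes 0.661, 0.669, 0.692 and 0.716.

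**If a visit means each weekly diary visit.** With 60% and 20% relapse and both scores missing in 2%, 5% or 10% of weeks, total events lost are 19%, 40% and 60%. Over six clinic visits at the same rates they are 6%, 14% and 26%.

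**The case against.** The strongest reply is that the prose only says which data count at a visit, while the table assigns dates and outcomes. On that reading a later relapse is an event, in line with Protocol 14.3.1 and Table 7-2. It is plausible, and the authors may have had only a missing tail in mind. But the sentence is itself a censoring instruction and states neither limit, so the conflict stands. The COVID-19 sensitivity analysis in SAP 10.1.2 does not settle it: it is conditional and covers only COVID-19 absences.

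The trigger is narrow, and this stands. PP NRS is a daily home diary, so a missed clinic visit does not remove it, and fewer than 4 of 7 days must be available before it counts as missing (SAP 10.2.2). IGA can also be picked up elsewhere: "All visits including unscheduled and early termination visits will be windowed based on the analysis visit window". True rates may well be near the low end.

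It also stands that placing every relapse at a clinic visit overstates the Kaplan-Meier effect, about fourfold compared with the all-diary limit. Both limits are therefore shown.

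The silence of SAP section 14 carries little weight, because Protocol 14 leaves the detailed definition of analysis variables to the SAP.

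The other date differences are minor. IGA is scheduled at Week 24, so the completer date usually coincides with the last assessment. Protocol 7.3 counts follow-up as part of study completion, so the SAP row may even be a clarification.

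**Conclusion.** The section contradicts itself on the primary endpoint and should be corrected. Followed literally, the prose discards relapses observed after an intermittent gap. With 50% placebo relapse, across both-missing rates of 0.25%, 1%, 3% and 5% per clinic visit, the loss is about 0.6–0.8%, 2.4–3.1%, 6.9–9.1% and 11.3–14.7% of placebo relapses. The placebo Kaplan-Meier estimate reads low by about 0.02–0.09, 0.1–0.4, 0.3–1.1 and 0.4–1.9 percentage points. All these rates are assumed, and losses could be larger if a visit means each diary week.

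A reader might infer that the rule biases the treatment comparison, or that it hides relapses because subjects stay away when they flare. The documents support neither. The hazard ratio is little affected when missingness is alike in both arms, and nothing suggests that it differs. A documented relapse is the route back to the extension study (Protocol 7.1), which gives a flaring subject a reason to attend. If absence were related to relapse, the placebo curve would read lower still, but that is a direction only. Nor do the documents show that the authors intended to drop later relapses; they simply do not address the case.

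**What to change.** In the SAP, before unblinding:

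1. Define the visit in the both-missing sentence: scheduled clinic visit or weekly diary analysis visit.
2. Keep subjects with an intermittent both-missing gap at risk, and count relapse at the first available assessment that meets either criterion.
3. Censor for missing data only when there is no later efficacy assessment, at the last efficacy assessment, and add a matching table row.
4. As minor alignment, make the prohibited-medication prose match the table and Table 7-2, and align the completer row with Protocol 14.3.1. Define the last efficacy assessment once: the later of the two scores, or the last date with both. The Protocol Synopsis joins the two scores with 'or'; Protocol 6.2.1 uses 'and'.

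The cost is SAP wording. No new data, visits or subjects are needed, and no protocol amendment, since the SAP supersedes. The downside is that a relapse first seen after a gap is dated late, by about 4 weeks per missed clinic visit; an interval-censored sensitivity analysis could address this and is optional.

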COVID-19=coronavirus disease 2019; JAK=Janus kinase; NK=neurokinin; PDE-4=phosphodiesterase-4; PN=prurigo nodularis; PUVA=psoralen+ultraviolet A; UVB=ultraviolet B.

If a prohibited therapy becomes necessary for the safety of the subject, the Investigator should notify the Medical Monitor and discuss possible alternatives. If a subject receives a prohibited therapy during the clinical study (e.g., inadvertent short-term use), the Investigator should also notify the Medical Monitor and discuss whether or not it is acceptable for the subject to continue receiving the study drug.

It is recommended that all subjects should be up to date with respect to standard of care vaccinations as defined by the local guidance. For subjects who have vaccination planned during the study, it will be determined after consultation with the treating physician, whether the administration of vaccine can be postponed until after the end of study without compromising the health of the subject. See also Section 9.6.1.

Vaccinations during the study and follow-up period are not permitted, with the exception of the specified non-live vaccines in Section 9.6.1.

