Treatment discontinuation	While on Treatment Strategy	Any data collected after a treatment discontinuation will be censored
Use of prohibited medication	While on treatment strategy	Any data collected after a use of prohibited medication will be censored

Table 7-2: Estimands for primary Endpoint

Endpoints	Estimands
Time to relapse meeting at least 1 of the defined criteria*	Treatment: randomized treatment with subcutaneous injections of nemolizumab or placebo at Week 0, 4, 8, 12, 16, and 20
	Population: ITT population
	Endpoint: Time to relapse meeting at least 1 of the defined criteria
	Intercurrent events: Time to relapse will be censored at the last observation prior to treatment discontinuation or use of prohibited medication

This document is confidential.

Endpoints	Estimands
	Summary measure: Hazard ratio of nemolizumab and placebo

*the time to relapse which is defined as meeting at least 1 of the following criteria:

- Increase in (weekly average of the) PP NRS score ≥ 4 points from baseline
- Increase in IGA score ≥ 2 points from baseline

This document is confidential.

8. General Aspects for Statistical Analysis

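### SAP 10.1.1 and the Section 7 estimand disagree on prohibited medication, so a relapse after such use can be an event or censored

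*SAP*

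**What the plan says.** SAP 10.1.1 treats prohibited medication twice. The prose before the model description says: "If a subject has taken prohibited medication at any point of time during treatment period, then subject will be censored at the respective visit". It makes no exception for relapse and does not define the visit meant. The censoring table below it codes "Relapse as described" as an event on the relapse date. A separate row, "Prohibited medication without relapse", is censored at "Date of last efficacy assessment (PP NRS and IGA) prior to prohibited medication".

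SAP Section 7 has its own rule. Table 7-1 names a while-on-treatment strategy and adds: "Any data collected after a use of prohibited medication will be censored". Table 7-2 says: "Time to relapse will be censored at the last observation prior to treatment discontinuation or use of prohibited medication". Neither depends on whether relapse occurred. Protocol Table 8 gives the same rule as Table 7-2. Protocol 14.3.1 also says that "subjects receiving any prohibited therapies will be censored from the primary analysis", without giving a date.

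Prohibited use does not always end participation. Protocol 9.6.3 has the investigator and the Medical Monitor "discuss whether or not it is acceptable for the subject to continue receiving the study drug".

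**The concern.** Status and time for the primary endpoint should follow from one rule. Here a subject who takes a prohibited medication, continues, and then meets a relapse criterion falls under several rules that give different answers. The prose censors at a visit that may come after the medication, which credits relapse-free time spent on it. The table's relapse row, read literally, counts the later relapse as an event. The estimand tables stop the clock before the medication. The first two readings depart from the SAP's own while-on-treatment strategy. About 40 subjects are expected (SAP 4.3; Protocol 14.1), so a few reclassified records could matter, and as written the choice is left to programming.

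**Working it through.** The documents state no power, event count or relapse rate, so there is no figure of theirs to reproduce. The check compares the rules on one subject and then illustrates materiality under assumptions.

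**One subject through each rule.** Target days come from SAP Table 8-1: Week 8 is Day 57 and Week 12 is Day 85. Suppose there is no relapse at Day 57, prohibited medication starts on Day 70, study drug continues, and the IGA criterion is met at Day 85.

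| Rule | Status | Day |
|---|---|---|
| 10.1.1 table, relapse row read literally | Event | 85 |
| 10.1.1 prose, visit = next visit | Censored | 85 |
| 10.1.1 prose, visit = analysis window containing Day 70 (Week 8, Days 43 to 70) | Censored | 57 |
| 10.1.1 table, medication row, if it means no relapse before the medication | Censored | 57 on IGA |
| Tables 7-1 and 7-2 | Censored | 57 on IGA; later on PP NRS |

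- Gap between censoring dates on IGA visits: 85 − 57 = 28 days.
- On weekly PP NRS (SAP Table 8-2), the last window wholly before Day 70 is Week 9, Days 57 to 63. Censoring at the end of that window gives a gap of 85 − 63 = 22 days. If a single daily entry counts, Day 69 gives 85 − 69 = 16 days.
- Follow-up credited after the medication under the next-visit reading: 85 − 70 = 15 days.
- A medication start one day later, Day 71, falls in the Week 12 window (71 to 98), so both readings of the prose then give Day 85.

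**Precedence.** Protocol Section 14 ranks the SAP above the protocol. Nothing ranks one SAP passage above another.

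**Materiality, under assumed rates only.** Simulation inputs: N = 40 randomized 1:1; exponential relapse times; 4-weekly visits; Cox model with treatment only; two-sided 5% Wald test; 1,500 replicates. Assumed 24-week relapse is 60% on placebo and 20% or 30% on nemolizumab. An assumed share of relapsers takes the medication in the interval before the relapse visit. Those relapses are (A) events, (B) censored at the relapse visit, or (C) censored one visit earlier. Event totals add the two arms, for example 12.0 + 4.0 = 16.0 and 9.7 + 3.2 = 12.9.

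| Relapse, placebo/nemolizumab | Relapsers with prior medication, placebo/nemolizumab | Events, A → B or C | Median HR, A / B / C | Share significant, A / B / C |
|---|---|---|---|---|
| 60% / 20% | 20% / 20% | 16.0 → 12.9 | 0.24 / 0.24 / 0.24 | 0.73 / 0.58 / 0.60 |
| 60% / 20% | 40% / 10% | 16.0 → 10.8 | 0.24 / 0.36 / 0.34 | 0.73 / 0.26 / 0.31 |
| 60% / 30% | 20% / 20% | 17.9 → 14.3 | 0.40 / 0.40 / 0.39 | 0.43 / 0.33 / 0.34 |
| 60% / 30% | 40% / 10% | 17.9 → 12.5 | 0.39 / 0.60 / 0.57 | 0.46 / 0.11 / 0.14 |

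Event versus censored (A against B or C) moves the median HR by at most 0.60 − 0.39 = 0.21, when use is unequal. The date alone (B against C) moves it by at most 0.60 − 0.57 = 0.03. With N = 100, the figure in SAP 4.1, the pattern is the same and the largest date effect is 0.60 − 0.56 = 0.04. The Monte Carlo standard error of a share is at most √(0.25/1500) = 0.013.

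The simulation gives medication only to subjects who go on to relapse, lets all of them continue, and gives the medication no effect on relapse. It shows how far the rules can diverge. It is not a forecast, and it does not show which rule is better.

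**The case against.** The strongest reply is that the intended rule can be recovered. Table 7-2 and Protocol Table 8 both censor before the medication without condition. Read with them, the table's row means no relapse before the medication, and the prose is one loose sentence out of line. That reading is plausible, and it supports deleting the sentence. It does not remove the problem, because 10.1.1 never says so and a programmer working from its literal rows can code an event.

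The case is also narrower than it first looks. Protocol 8.3 lists non-permitted therapy as a reason to stop study drug unless otherwise agreed, and the censoring table's treatment-discontinuation row carries no relapse condition. Only subjects allowed to continue are clearly exposed to the conflict. The per-protocol analysis is a partial check: Protocol 15.7.2 lists prohibited therapy as a major-deviation category, and SAP 6.5 decides exclusions case by case. That analysis may drop such subjects, but it does not test the censoring rule.

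A reader might infer more: that the prose, by covering use at any time in the treatment period, erases a relapse that came before the medication. The documents do not support this. The prose sets only a censoring time. If relapse came first, the ordinary derivation takes the earlier of event and censoring; the table codes relapse as an event; and relapse leads to exit from the study (Protocol 7.1 and 9.6.2). What remains is that the order should be written down.

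**Conclusion.** The point holds. Within 10.1.1 the prose and the table disagree on the censoring date and on whether a relapse after the medication counts, and both can depart from Tables 7-1 and 7-2. For a subject who continues after prohibited medication and then relapses, status can be event or censored. The censoring date can differ by up to about one visit interval on IGA visits, and by less if PP NRS defines the last assessment.

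The effect on the hazard ratio depends on how many subjects follow this course and in which arm, and the documents give neither. No percentage of lost information is claimed, because there is no stated event count to base it on. Under the assumed rates, equal use left the median HR almost unchanged but reduced the share of significant results. Unequal use moved both. The choice of censoring date was minor throughout. The rule should be settled before unblinding.

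**What to change.** Delete the prose sentence on prohibited medication in SAP 10.1.1. Replace the table row with two ordered statements that match Table 7-2:

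- *Prohibited medication started before the relapse date, whether or not relapse follows: censored at the last efficacy assessment before the start date.*
- *Relapse dated before the start of prohibited medication: event.*

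Then add three clarifications:

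1. How a PP NRS relapse is dated when its 7-day window straddles the medication start (for example Days 64 to 70 with a start on Day 70). One option in keeping with Table 7-1 is to use only windows that end before the start date.
2. How relapse and medication start on the same day are treated.
3. Whether the last efficacy assessment means either instrument or both. The estimand in the protocol synopsis joins IGA and PP NRS with 'or'; Protocol 6.2.1 uses 'and'.

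Refer to this order from Tables 7-1 and 7-2. The cost is a few sentences in the SAP before unblinding. No data collection or clinical management changes.
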